9.1.3 OL-300 Analyses

Exposure duration will be summarized overall and for each age group, in total by initial treatment group (placebo/dose level/overall active) for the analyzed OL-300 period as well as for the overall treatment period for the OLS-300.

Mean daily exposure, defined as the total number of hours of application during the analyzed OL-300 period divided by the number of days in that period, will be summarized for the OLS-300.

Number of days with patch not applied, defined as the total number of days with null daily duration of application, will be summarized as a continuous variable overall and for each age group, in total and by actual treatment group (placebo/dose level/ overall active) for all subjects during the analyzed OL-300 period as well as for the overall treatment period.

Reasons for patches not applied per protocol will be summarized overall and for each age group, in total by initial treatment group (placebo/dose level/overall active) for the analyzed OL-300 period as well as for the overall treatment period for the OLS-300.

9.2 TREATMENT COMPLIANCE

9.2.1 General

The overall compliance, based on the Study Drug Accountability Form, is calculated from the total number of patches dispensed and returned by subject

$$\frac{(\text{number of patches dispensed} - \text{number of patches returned})}{\text{number of days during the corresponding period}}$$

This document is confidential

Statistical Analysis Plan

For overall compliance, number of days during the corresponding period is defined as treatment exposure; otherwise, period is defined as the number of days between visit (n) and visit (n-1)

Compliances exceeding 100% will be set to 100%.

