4.3.2 Exclusion Criteria

1. Any new disorder or disease that may affect the subject's participation in the study, or place the subject at increased risk, or for which epinephrine use is contraindicated.
2. Poor compliance in patch application (below 80%), defined as patch not applied at all for >73 days (either consecutive or not) during the second year of participation in MILES.

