6.6 Treatment Compliance

Subjects and/or parent(s)/guardian(s) will receive diary cards to record the daily application of Viaskin patches (see [Section 7.3.2.12](#) for further details about diary cards). The duration of the patch application will be recorded every day from Day 1 (Visit 4) up to Month 3 (Visit 9) on the subject diary cards. After Month 3, the subjects will only record the days and time periods when the duration of the patch application did not follow the durations recommended in the protocol. During the period of 24 hours of daily application, flexibility between 20 to 28 hours of daily application is permitted. If a Viaskin patch is removed prematurely or falls off, the daily duration of application of the patch and the reason for early removal will be recorded in the subject diary cards. The data recorded in the diary card by the subject and/or parent(s)/guardian(s) will be collected periodically during the subject's visit at sites and entered into the eCRF or the clinical database.

It is the Investigator's responsibility to correctly instruct subjects and/or parent(s)/guardian(s) on how to store and administer the investigational product. At each visit, prior to dispensing a new investigational treatment box, the compliance of the subject will be assessed by evaluating the number of days the patches were applied (even for a duration that is less than the recommended duration), *versus* the number of days in that time interval. An overall compliance of $\geq 80\%$ over the treatment period is sought. Subjects exhibiting a poor compliance ($< 80\%$) should be counseled on the importance of a good compliance.

The Investigator or designated study personnel will maintain a log of all investigational product dispensed (see [Section 10.1](#), Drug Accountability for details).

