9.1 EXTENT OF EXPOSURE

9.1.1 General

Extent of exposure was summarized using the exposure duration in the respective period, regardless of temporary interruptions, defined as:

Date of last patch application in the period - date of first patch application in the period + 1.

This document is confidential

Statistical Analysis Plan

Duration of patch application is assessed as recommended or not every day from Day 1 (Visit 4) up to Month 3 (Visit 9) on the subject diary cards. If duration of application is not as recommended, actual duration is recorded in hours and minutes per day. After Month 3 (Visit 9), application not as recommended were registered; actual duration is recorded in hours and minutes per day. Duration will be imputed with the recommended duration (6, 12 or 24 hours) for each day with duration assessed as 'as recommended'.

Reasons for patches not applied per protocol were classified a-posteriori in the randomized blinded treatment period (ITT) and the Viaskin Milk 500 μ g open-label period (OLS-500). The main reasons for patches not applied as per protocol, were subsequently pre-specified in the subjects' diaries as follows:

- Fell off
- Discomfort
- Personal convenience
- Investigator's decision
- Forgot
- Other

Inconsistencies in the data of diary cards are very common in clinical studies. In general the worst-case principle will be applied. Details of handling the different cases will be documented in a respective note-to-file document.

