9.2.1 Double-blind Month 12 and OL-500 analyses

The number of subjects with a compliance $\geq 80\%$ was presented. An overall compliance of $\geq 80\%$ is defined as good compliance.

Compliance at each visit was calculated during the double blind period in a similar way and summarized. Subjects' compliance overall and by visit was summarized overall and for each age group, in total and by randomized treatment group (placebo/dose level/overall active) for the randomized blinded treatment period (Months 0 to 12).

It was repeated for the Viaskin Milk 500 μ g open-label treatment period (Months 12 to switch to Viaskin Milk 300 μ g) and the whole treatment period (Months 0 to switch to Viaskin Milk 300 μ g).

Poor compliance in patch application (below 80%), defined as patch not applied at all for >73 days (either consecutive or not) during the second year of participation in MILES is defined as an exclusion criterion for the extension part of the study and was summarized.

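### Overall compliance is divided by the days from first to last patch applied, so untreated days after a child stops patches but stays in the study drop out of the figure

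*SAP*

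**What the plan says.** SAP 9.2.1 (General) bases overall compliance on drug accountability: it "is calculated from the total number of patches dispensed and returned by subject", divided by a number of days. Two rules complete it: "For overall compliance, number of days during the corresponding period is defined as treatment exposure", and "Compliances exceeding 100% will be set to 100" per cent. For compliance at a visit, the denominator is instead the days between consecutive visits.

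The only definition of exposure duration in the SAP is in 9.1.1: "Date of last patch application in the period - date of first patch application in the period + 1", taken "regardless of temporary interruptions".

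The next subsection, on the double-blind Month 12 and OL-500 analyses, states that overall compliance of at least 80% "is defined as good compliance" and counts the subjects who reach it. It also tabulates the extension criterion from Protocol 4.3.2, which equates compliance below 80% with "patch not applied at all for >73 days (either consecutive or not", in the second year of participation. The OL-300 subsection (SAP 9.2.2) says only that compliance will be summarised.

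Protocol 6.6 says that compliance at each visit "will be assessed by evaluating the number of days the patches were applied", set against the days in that interval, and it seeks at least 80% over the treatment period.

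**The concern.** An exposure-based denominator treats two kinds of missed patch differently. A gap followed by resumption stays in the denominator and lowers compliance. A stop with no resumption removes its own days from the denominator and lowers nothing, however long it lasts. For a patch meant to be worn daily for a year or more, stopping and staying in follow-up is an ordinary way of not complying. The documents allow it: Protocol 6.6 calls for counselling of poor compliers, and Protocol 4.5 makes noncompliance only a possible reason for discontinuation.

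At stake is what a reader takes from the overall compliance figure and, for the blinded and OL-500 periods, from the count of good compliers. Both will be read as describing how fully the period was treated. A child challenged after months without patches can appear in them as fully compliant.

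**Working it through.** **Inputs.** Numerator, cap and denominator rule: SAP 9.2.1. Exposure duration: SAP 9.1.1. The 80% label and the 73-day rule: SAP, double-blind and OL-500 compliance subsection, and Protocol 4.3.2. Period lengths of 364 and 365 days and the stop days are illustrative assumptions. The first patch is on day 1.

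**Step 1: the plan's own figure.** 73/365 = 20.0%, so 73 unapplied days leave (365 − 73)/365 = 80.0%, and 74 leave 291/365 = 79.7%. The equation of more than 73 days with less than 80% works only if the denominator is the whole year.

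**Step 2: the two formulas.**
- SAP overall compliance = min(100%, (dispensed − returned) / (last patch day − first patch day + 1)).
- Planned-period compliance = patches used / days on which a patch was due.

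**Step 3: daily wear, then a stop, leftover patches returned, child stays to the end.**

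| Period (days) | Last patch on day | SAP overall | Planned period |
|---|---|---|---|
| 364 | 182 | 182/182 = 100% | 182/364 = 50.0% |
| 365 | 90 | 90/90 = 100% | 90/365 = 24.7% |
| 365 | 270 | 270/270 = 100% | 270/365 = 74.0% |
| 365 | 291 | 291/291 = 100% | 291/365 = 79.7% |
| 365 | 292 | 292/292 = 100% | 292/365 = 80.0% |

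In a 365-day period, any stop before day 292 after daily wear moves from good to below 80% when the denominator is the planned period.

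**Step 4: incomplete wear before the stop.** With 146 patches used by day 182 (about 80% wear), the SAP gives 146/182 = 80.2%, still labelled good. The planned period gives 146/365 = 40.0%. The SAP figure is thus compliance up to the last patch, and it is 100% only if wear was complete until then or leftovers were not returned.

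**Step 5: leftovers kept.** After a stop at day 90 with 92 patches unreturned, the numerator is 90 + 92 = 182. The ratio 182/90 is capped at 100%.

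**Step 6: the contrast.** A gap on days 91–182 followed by resumption gives 273/365 = 74.8%. A stop at day 90 with one further patch on day 365 gives 91/365 = 24.9%, against 100% without that patch.

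**Step 7: conflict within the SAP section.** A child who stops at day 182 of the second year has 365 − 182 = 183 days without a patch in that year. That is more than 73, hence poor compliance under one rule. Under the other, those 183 days do not enter the denominator if no patch is applied later in OL-500.

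**Step 8: what by-visit compliance shows.** With Visits 10, 11 and 12 on target days 182, 274 and 365 (SAP Table 3), a stop at day 182 with leftovers returned gives 0/92 and 0/91, or 0% in both later intervals.

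**The case against.** Reporting compliance while on treatment separately from duration of treatment is a defensible choice, and the SAP does report duration. Exposure duration is summarised for every period, with six-month classes in OL-500. Days without a patch are summarised for every period. By-visit compliance in the blinded and OL-500 periods uses the days between visits, which is the Protocol 6.6 basis. Protocol 6.6 gives no formula for its 80% aim over the treatment period, and SAP Table 1 runs the whole treatment period from first to last treatment. SAP 9.2.1 does not cross-refer to 9.1.1. Compliance is checked at visits, and compliance below 80% bars both the extension and the switch to 300 µg.

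Most of this stands as a limit on the consequences. A reader might infer that stopping is hidden throughout the plan, but the summaries just listed partly reveal it. They do not fully replace the overall figure. No by-visit compliance summary is specified for OL-300. After Month 3 the diary records only departures from the recommended wear, so a family that abandons both patch and diary may leave no record of untreated days; that last step is an inference. Exposure duration alone cannot separate a child who left from one who stayed untreated.

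The objection does not rescue the overall figure as labelled. It is not called compliance while on treatment, it carries the good-compliance label, and it sits beside a 73-day rule that needs a full-year denominator. Table 1 uses visit-based ends for the blinded, OL-500 and OL-300 periods. SAP section 12, which lists changes from the protocol's analyses, does not mention compliance.

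**Conclusion.** The point holds for the overall compliance summaries. For a child who stops and stays, the SAP figure exceeds planned-period compliance by an amount that grows with the length of the stop: 100% against 50% for a mid-period stop after full wear, and 80.2% against 40.0% after about 80% wear. This rests on reading treatment exposure as the exposure duration of SAP 9.1.1, the only definition given, and on the child remaining in the study. How many children are affected cannot be told from the documents.

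Three stronger readings are not supported:
- That every child who stops scores 100%. This needs complete wear up to the stop, or unreturned patches.
- That the per-protocol sets or the primary result are distorted. SAP section 5 forms the per-protocol sets by review of deviations, under specifications kept in separate documents, and nothing ties them or the Month 12 responder analysis to this figure.
- That a good-compliance count is wrong for OL-300. The SAP specifies that count only for the blinded and OL-500 periods.

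**What to change.** In SAP 9.2.1, define the overall denominator as the days from the first patch of the period to the last day a patch was due, or to the study discontinuation date if earlier. The last day due would be:

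- **Blinded period:** the day before Visit 12 (Protocol 6.3.1).
- **OL-500:** VS1 (SAP Table 1). For subjects ending at Month 24 without switching, the day before Visit 17 (Protocol 6.3.2), or before Visit 16 where Visit 17 was dropped under Amendment 5.
- **OL-300:** VS3/VS4 for the Year 1 analysis (SAP Table 1), and the day before VS6 or VS7 at the end, according to whether the optional challenge was done (Protocol 6.3.2).

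Apply this prospectively to OL-300, whose analyses are still written in the future tense. For the blinded and OL-500 periods, whose analyses have already been run, add it as a supplementary rerun, including the count at 80% or more, and relabel the present figure as compliance while on treatment. Report subjects whose product was permanently stopped for an adverse event separately, so that their later days are not read as non-compliance. Leave the by-visit calculation unchanged.

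The cost is a short SAP change, a rerun of descriptive tables that is post hoc for the two completed periods, and somewhat less favourable compliance figures. No efficacy analysis changes.

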9.2.1 Double-blind Month 12 and OL-500 analyses

The number of subjects with a compliance $\geq 80\%$ was presented. An overall compliance of $\geq 80\%$ is defined as good compliance.

Compliance at each visit was calculated during the double blind period in a similar way and summarized. Subjects' compliance overall and by visit was summarized overall and for each age group, in total and by randomized treatment group (placebo/dose level/overall active) for the randomized blinded treatment period (Months 0 to 12).

It was repeated for the Viaskin Milk 500 μ g open-label treatment period (Months 12 to switch to Viaskin Milk 300 μ g) and the whole treatment period (Months 0 to switch to Viaskin Milk 300 μ g).

Poor compliance in patch application (below 80%), defined as patch not applied at all for >73 days (either consecutive or not) during the second year of participation in MILES is defined as an exclusion criterion for the extension part of the study and was summarized.

9.2.2 OL-300 Analyses

Compliance will be summarized overall and for each age group, in total by initial treatment group (placebo/dose level/overall active) for the analyzed OL-300 period as well as for the whole treatment period for the OLS-300.

9.3 ADVERSE EVENTS

9.3.1 Definitions

Treatment emergent AEs (TEAEs) are defined as any AEs, regardless of relationship to investigational product which occur during or after the initial patch application (or any event already present that worsens in intensity following exposure to the patch).

AEs with missing or incomplete onset date will be treated as TEAEs and missing onset date will be imputed as date of initial patch application unless there is evidence that the event occurred prior or after the treatment period, e.g. year and month indicate the onset date is before study treatment.

AEs will be considered drug-related if relationship information is definite / probable / possible. If relationship information is missing for a TEAE, the AE will be considered as drug-related.

This document is confidential

Statistical Analysis Plan

If the severity is missing of an AE starting prior to the date of initial patch application, then a severity of "Mild" will be assigned. If the severity is missing of an AE starting on or after the date of initial patch application, then a severity of "Severe" will be assigned.

Imputed values for relationship, severity or onset date will be used for incidence summaries, while the actual values will be used in data listings.

9.3.2 General

All AEs and TEAEs were listed and tabulated by Medical Dictionary for Regulatory Activities (version 17.0 or higher) System Organ Class (SOC) and preferred term. Incidence tables will be presented for all TEAEs and TESAEs.

For adverse events analyses, serious adverse events occurring during DBPCFC were not considered, they were described separately (see [section 9.3.4](#)).

9.3.3 Double-blind Month 12 and OL-500 analyses

9.3.3.1 Overview tables

An overview of AEs and an overview of TEAEs, occurred in the SS of the randomized treatment period (incl. screening), presented the number of subjects and number of respective events overall and for each age group, in total and by treatment group (placebo/dose level/overall active) with

- Any AE /TEAE,
- Any serious AE/TEAE,
- Any TEAE considered related to the investigational product (IP), and
 - Any TEAE definitely related,
 - Any TEAE probably related,
 - Any TEAE possibly related,
 - Any TEAE unlikely related,
 - Any TEAE not related
- Any TEAE considered not related to IP, and
 - Any TEAE unlikely related,
 - Any TEAE unrelated,
- Any serious TEAE considered related to IP,
- Any TEAE leading to treatment discontinuation,
- Any AE/TEAE leading to death,
- Any mild AE/TEAE,
- Any moderate AE/TEAE
- Any severe AE/TEAE,
- Any severe TEAE considered related to IP.

This document is confidential

Statistical Analysis Plan

- Any application site disorder³ considered related to IP
- Any severe application site disorder considered related to IP
- Any Adverse Events of specific interest (AESI)
- Any local AESI⁴
- Any systemic AESI⁵
 - Considered related to IP
 - Considered unrelated to IP
- Any TEAE leading to an epinephrine intake
 - Considered related to IP
 - Considered unrelated to IP
- Any TEAE leading to systemic or inhaled corticosteroids use
 - Considered related to IP
 - Considered unrelated to IP
- Any TEAE leading to topical corticosteroids use
 - Considered related to IP
 - Considered unrelated to IP

Similar overviews for TEAEs were performed for the whole treatment period as well as for the Viaskin Milk 500µg open-label treatment period, by the initial actual treatment-group.

The overviews of the TEAEs were repeated for the 2 filaggrin mutation subgroups in the Month 12 analysis. These analyses will not be provided for the Viaskin Milk 500µg open-label treatment period analysis.

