2.2 TIMINGS OF ANALYSES

2.2.1 Primary analysis and subsequent analyses

The primary analysis of safety and efficacy was performed at the end of the double-blind period, after all randomized subjects had completed the Month 12 Double-Blind Placebo-Controlled Food Challenge (DBPCFC), or withdrew.

After month 12, all subjects continued treatment with Viaskin Milk 500 μ g dose in an open-label manner for up to a maximum of 36 additional months. After the analysis of the double-blind period that showed the best efficacy with the Viaskin Milk 300 μ g dose, subjects were switched to the 300 μ g dose and continued treatment for two additional years.

Following the month 12 double-blind period primary analysis, three subsequent analyses will be conducted during the open-label treatment periods:

1. OL-500 period analysis: when all randomized subjects completed the Viaskin Milk 500 μ g open-label period, or withdrew.
2. OL-300 period Year 1 analysis: when all randomized subjects completed one year of Viaskin Milk 300 μ g open-label period, or withdrew (see [Table 1](#)).
3. OL-300 period (Year 2) final analysis : when all subjects completed the End of Study (EOS) visit, or withdrew. The complete analysis as described in this SAP will be performed.

This current SAP v7.0 describes in particular the analyses that will be done for the first year and at the end of the OL-300 period.

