3.1 BRIEF DESCRIPTION

MILES study (V135-201) is a multi-centre, double-blind, placebo-controlled, randomized trial to study the safety and efficacy of Viaskin Milk applied epicutaneously every day to subjects from 2 to 17 years of age with IgE-mediated cow's milk allergy (CMA). Viaskin Milk is a patch containing an extract of cow's milk proteins. The placebo treatment consists of a Viaskin Milk patch containing a similar formulation without cow's milk proteins.

Subjects received blinded treatment for 1 year at one of the 3 doses of Viaskin Milk: 150 μ g, 300 μ g, or 500 μ g, or placebo. After the first year, all subjects received the highest dose of Viaskin Milk 500 μ g, and continued treatment in an open-label manner for up to a maximum of 3 additional years. Following results of the 12-month blinded period, all eligible subjects who wish to continue participation in the study were switched from Viaskin Milk 500 μ g to Viaskin Milk 300 μ g dose for 24 additional months of treatment.

The study is conducted at 17 sites in the United States and Canada, with selected investigators and staff experienced in the diagnosis and management of CMA and anaphylaxis, and who are capable of performing a DBPCFC in children (2 to 11 years old) and adolescents (12 to 17 years old).

Eligible subjects with confirmed IgE-mediated CMA performed a first DBPCFC at screening with escalating doses of cow's milk proteins. Subjects showing a positive DBPCFC at screening, defined as the appearance of objective signs or symptoms to an eliciting dose of cow's milk proteins \leq 300 mg (approximately 9.4 mL of cow's milk) were randomized in the study.

The study was divided into 2 consecutive parts for randomization of the subjects to treatment: Part A and Part B. Part A permitted an evaluation of the safety of 3 escalating doses of Viaskin Milk (150 μ g, 300 μ g, and 500 μ g cow's milk proteins) versus placebo in successive cohorts of subjects prior proceeding to Part B. Part B was designed to evaluate the efficacy and safety of the 3 selected safe doses (as determined from Part A) of Viaskin Milk versus placebo.

The efficacy of Viaskin Milk was assessed based on data pooled from subjects in both Part A and Part B. Details of subject enrolment and the treatments administered for each part of the study are provided in [Section 3.4](#).

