6 GENERAL ASPECTS FOR STATISTICAL ANALYSIS

6.1 GENERAL METHODS

6.1.1 General

All analyses and summaries will be produced using CCI [REDACTED]

Unless otherwise specified, summaries will be presented overall and for each age group, in total and by treatment (placebo/dose level/overall active). "Overall active" is a synonym for "All Doses Viaskin Milk". In the OL-period(s) analyses, it is defined as the subjects who were randomized / treated in one of the 3 Viaskin Milk doses for the double-blind treatment period.

The secondary and explorative efficacy endpoints, referring to "Change to Baseline" are all analyzed with respect to "Month 0". If not specified otherwise, summaries for changes from baseline indicate summaries relative to "Month 0" as well as relative to "Month 12", see [section 6.2.1](#) for definition.

Unscheduled assessments will not be included in summary tables unless specified otherwise, but will be included in the subject listings.

In case of repeated measurements in the scheduled time-windows, the first measurement will be used for analysis, if not specified otherwise.

Early termination assessments will be analyzed as having occurred at the next scheduled assessment.

All tables, listings and figures will include footers that identify the name of the program that created the item, together with the date and time on which it was created. Headers will include the total number of pages that the presentation contains and, for each page, the number of the page within the presentation.

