9.3.3.2 Incidence tables

The following tabulations were produced overall and for each age group, in total and by treatment group (placebo/dose level/overall active) on the SS for the randomized blinded treatment period.

- TEAEs overall and by system organ class and preferred term
- TEAEs by maximum severity, overall and by system organ class and preferred term
- Severity of TEAEs, overall and by system organ class and preferred term
- Severe TEAEs, overall and by system organ class and preferred term
- Severe TEAEs considered related to IP, overall and by system organ class and preferred term

³ Application site disorders are AEs with 'Application and instillation site reactions' in their MedDRA-coded HLTs.

⁴ Local AESI are identified as detailed in [Section 16.1 Appendix 1](#).

⁵ Systemic AESI are identified as detailed in [Section 16.2 Appendix 2](#).

Statistical Analysis Plan

- TEAEs considered related to investigational product (IP), overall and by system organ class and preferred term
- Number of TEAEs considered related to IP by maximum severity, system organ class and preferred term
- TESAEs overall and by system organ class and preferred term
- TESAEs considered related to IP, overall and by system organ class and preferred term
- Adverse Events leading to treatment discontinuation overall and by system organ class and preferred term
- Application site disorders considered related to IP overall and by system organ class and preferred term
- Treatment emergent systemic AESI overall and by system organ class and preferred term
- Treatment emergent systemic AESI considered related to IP overall and by system organ class and preferred term
- Treatment emergent local AESI overall and by system organ class and preferred term

They were repeated overall and for each age group, in total and by initial actual treatment group on the SS for the whole treatment period, and on the OLS-500 for the Viaskin Milk 500 μ g open-label treatment period :

Additionally, tables showing the number and percentage of subjects who experienced at least one TEAE and the number of events by SOC and PT, summarizing TEAEs leading to:

- Epinephrine use:
 - o Standard medication name that contains "EPINEPHRINE" and ATC level 1 = "CARDIOVASCULAR SYSTEM"
- Systemic or inhaled corticosteroid use,
 - o ATC code starting with "H02", "R03AK", "R03BA"
- Topical corticosteroid use,
 - o ATC code starting with "D07"

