9.3.3.3 Subject-Year Analysis

A subject-year analysis was performed on the same parameter as described for the overview tables above on the whole treatment period overall and for each age-group for the SS. The subject year analysis should be presented according to treatments received (not randomized). E.g., subject randomized as placebo and treated during one year with Placebo then treated with Viaskin Milk 500 μ g during 2 years should account for 1 patient-year in Placebo column and 2 patient-year in Viaskin Milk 500 μ g column.

This document is confidential

Statistical Analysis Plan

Additionally, a subject-year analysis presented the total number of subject-years, the number of subjects with a TEAE (respectively a TEAE considered related to IP) per subject-year and the number of TEAEs (respectively TEAEs considered related to IP) per subject-year, for each dose level and by SOC and PT on the whole treatment period overall and for each age-group for the SS.

Separate listings were performed additionally:

- SAEs
- TESAEs
- Adverse events of specific interest (AESI):
 - o Local AESIs.

These local TEAEs of interest will be identified following methodology described in [16.1 Appendix 1](#).

- o Systemic AESI considered related to IP.
- o Systemic AESI (whether related or not).

These systemic TEAEs of interest will be identified following methodology described in [16.2 Appendix 2](#).

- AEs leading to discontinuation
- TEAEs leading to epinephrine intake

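### Whole-treatment-period adverse event tables count ex-placebo subjects' events on active patches under placebo, and several of these tables by SOC and preferred term have no treatment-received counterpart

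*SAP*

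**What the plan says.** SAP 9.3.3.1 gives the overview of TEAEs first for the blinded period. It then adds: "Similar overviews for TEAEs were performed for the whole treatment period", with columns "by the initial actual treatment-group". SAP 9.3.3.2 does the same for the SOC and preferred-term tables: "They were repeated overall and for each age group, in total and by initial actual treatment group on the SS for the whole treatment period". Those tables include severity, TESAEs, discontinuations, and systemic and local AESI. The SOC and preferred-term tables of TEAEs leading to epinephrine or corticosteroid use are also repeated for the whole period, but no grouping is stated for that repeat.

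SAP 6.1.1 fixes the overall-active column for open-label analyses: "it is defined as the subjects who were randomized / treated in one of the 3 Viaskin Milk doses" in the blinded year.

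SAP 9.3.3.3 uses a different rule for the subject-year analysis ("The subject year analysis should be presented according to treatments received (not randomized"), and illustrates it with a subject who has one year of placebo and then two years of 500 µg. The opening of SAP 9 says that safety analyses generally follow the treatment actually given.

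The end of the whole treatment period is not settled. Table 1 in SAP 6.2.2 runs it from first to last treatment. The compliance text for the double-blind and OL-500 analyses in SAP 9.2 stops it at the switch to 300 µg. For the final analysis, SAP 2.2.1 says: "The complete analysis as described in this SAP will be performed".

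**The concern.** After Month 12 nobody receives placebo. Continuing subjects get 500 µg for up to 36 months and, if they switch, 300 µg for 24 months. In a table that covers the whole period by initial arm, a local reaction or an AESI of an ex-placebo subject in an open-label year is a placebo event. The placebo and active columns then move together even when the patch causes the event.

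The overall-active column describes only subjects who started on active, and the total column mixes in true placebo time. Neither is the incidence on active treatment among all who received it. Long-term safety is one of the study objectives, and these are the tables a reader would turn to for it.

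**Working it through.** **1. The SAP's own figure.** One year of placebo and two of 500 µg: 12/12 = 1 and 24/12 = 2 patient-years, as SAP 9.3.3.3 states. The active share of that subject's time is 24/36 = 67%. The longest course is 12 + 36 + 24 = 72 months, which matches the stated maximum of about 6 years.

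**2. Active share for other durations.** With m open-label months, the share is m/(12 + m).

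**3. Effect on a rate ratio read by initial arm.** Let R be the true active-to-placebo rate ratio (assumed constant, with equal follow-up in both columns). The ratio shown is R(12 + m)/(12 + mR).

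| Open-label months m | Active share | Shown if R = 1.5 | Shown if R = 2 | Shown if R = 3 |
|---|---|---|---|---|
| 6 | 33% | 1.29 | 1.50 | 1.80 |
| 12 | 50% | 1.20 | 1.33 | 1.50 |
| 24 | 67% | 1.125 | 1.20 | 1.29 |
| 36 | 75% | 1.09 | 1.14 | 1.20 |
| 60 | 83% | 1.06 | 1.09 | 1.125 |

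The last row requires the whole period to run to last treatment. If it ends at the switch, m cannot exceed 36 and the maximum share is 75%.

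**4. Effect on the percentage with at least one event.** Assume 12-month risks of 20% on placebo and 40% on active, with constant hazards. The placebo column shows 1 − 0.8 × 0.6^(m/12) and the active column 1 − 0.6^(1 + m/12).

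- Blinded year: 20% versus 40%, a difference of 20 points.
- m = 12: 52.0% versus 64.0%, 12.0 points.
- m = 24: 71.2% versus 78.4%, 7.2 points.
- m = 36: 82.7% versus 87.0%, 4.3 points.

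This narrowing is not merely both columns filling up. With three years of real placebo, the placebo figure would be 1 − 0.8³ = 48.8%, against 78.4% on active.

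**5. Subjects left out of overall active.** Part A has 2 placebo subjects in each of 3 cohorts, so 6. Part B has 180/4 = 45 if allocation was exactly equal. That is about 51 of 198 randomised, or 26%. The number who went on to active patches is not given and can only be equal or smaller.

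**6. What the planned tables cover.**

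| Output | Ex-placebo events on active patches |
|---|---|
| Blinded-period tables (9.3.3.1, 9.3.3.2) | None in the window; clean contrast |
| OLS-500 and OLS-300 tables | Active time only, ex-placebo subjects in the total column, but each covers one period |
| Subject-year rates, overview parameters (9.3.3.3, 9.3.4.3) | Assigned to the dose received |
| Subject-year rates by SOC and preferred term (9.3.3.3) | Assigned to the dose received, for TEAEs and related TEAEs only |
| Whole-period overview and SOC/preferred-term tables by initial group | Filed under placebo |

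Two gaps remain. Severity, TESAEs, AESI and discontinuations by SOC and preferred term have no treatment-received version over the whole period. No table gives cumulative incidence from first to last active patch in everyone exposed.

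**7. Check of an obvious remedy.** Suppose the placebo column held blinded time only and stood beside an any-active column of crude incidence. Take no drug effect at all, with an assumed 0.3 events per year everywhere. Placebo at 1 year shows 1 − exp(−0.3) = 25.9%. Any-active, with three quarters of subjects followed for 3 years (59.3%) and one quarter for 2 years (45.1%), shows 0.75 × 59.3 + 0.25 × 45.1 = 55.8%. The unequal windows alone would double the apparent risk.

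**The case against.** The strongest defence is that the placebo contrast lives elsewhere. Every overview and incidence table is first produced for the blinded year by treatment group, and nothing presents the whole-period repeats as a controlled comparison. For longer-term safety, Protocol 8.1.7.1 points to the subject-year analysis, which covers all the overview parameters by treatment received, including AESI, epinephrine and corticosteroid use, and discontinuation. The open-label tables contain active time only and include ex-placebo subjects. The initial-group choice is disclosed in SAP 12.3, and a summary by treatment sequence is legitimate. SAP 9.3.3 is also written in the past tense and retained for traceability.

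Most of this stands, and it limits the point. A reader might infer that the trial has lost its placebo-versus-active comparison of harms, or that attributable harm is hidden. The documents do not support that.

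What the defence does not remove are the two gaps in step 6, and a column headed placebo that contains active exposure. The past tense does not close the matter either, because the final analysis is to run the complete SAP.

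**Conclusion.** The point holds for the whole-treatment-period tables and no further. By initial group, they place events on active patches under placebo and leave ex-placebo subjects out of overall active. This is at odds with the SAP's general rule of analysing safety by the treatment given.

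For a subject with more than 12 open-label months, most of the time filed under placebo is active: 67% in the SAP's example and 75% at 36 months. The figure of 83% applies only if the period runs past the switch. At exactly 12 months the share is half, and a subject who stops in the blinded year contributes no active time. It would therefore be wrong to call the whole column mostly active without the follow-up data.

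Read as a contrast, the tables are biased towards no difference. They do not reach it: under constant rates the ratio shown stays above 1. The sizes in steps 3 and 4 rest on assumed rates and equal follow-up, since the documents give neither event rates nor the distribution of open-label duration. The practical loss is in the event types that lack treatment-received output by SOC and preferred term. It is a moderate point that can still be corrected for the final analysis.

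**What to change.** 1. In the whole-period tables of SAP 9.3.3.1 and 9.3.3.2, start the window at the first active patch for ex-placebo subjects. Label their column 'initially placebo, events on active only', and include them in overall active. State the grouping of the epinephrine and corticosteroid tables.
2. Extend the treatment-received rates per subject-year in SAP 9.3.3.3, by SOC and preferred term, to TESAEs, severe TEAEs, AESI, discontinuations and rescue-medication use.
3. State once whether the whole treatment period ends at the switch to 300 µg or at last treatment, and apply that throughout.
4. Do not set a 12-month placebo column beside a multi-year any-active column as crude incidence. Use exposure-adjusted rates for that comparison, and refer readers to the blinded-period tables for the placebo contrast.

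The cost is SAP wording and a re-cut of tables. No new data are needed, and the attribution rule is already specified for the subject-year analysis. The small downside is that these columns will no longer match the initial-group columns used elsewhere.
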